6.3.5 Follow-up of Patients with Discontinuation of Study Treatment

Patients who had an early discontinuation of study treatment will continue to be followed carefully through the 30-day study period unless consent is withdrawn. The follow-up may include the following:

- Additional safety laboratory tests and/or other investigations;
- Continued confinement in the ICU or hospital; and

Obtaining a specialist's opinion.

7 STUDY DRUG AND ADMINISTRATION

7.1 *Identity of Study Drug*

The chemical name for OCR-002 is ornithine phenylacetate; (L-ornithine·benzeneacetate salt (1:1), CAS-RN 952154-79-9). The molecular formula is C₈H₇O₂·C₅H₁₃N₂O₂.

7.2 *Packaging, Supply and Labeling of Study Drug*

The OCR-002 study drug will be supplied by Ocera Therapeutics, Inc. (Ocera) as a sterile small volume parenteral in single-use, 50 mL vials (200 mg/mL, 10g/vial) with a pH of approximately 6.6. Each vial contains a 1:1 molar concentration of ornithine phenylacetate in sterile water for injection with no other excipients.

The OCR-002 drug product in the vials must be diluted prior to use and is **NOT** intended for direct injection. The product will be supplied as a 4-fold hypertonic concentrate and requires dilution under aseptic conditions prior to use. Total volume of the i.v. infusion preparation is targeted to 500 mL.

Instructions will be provided to the clinical study site by Ocera that will further detail the preparation, labeling, and storage of OCR-002 in a Manual of Operations. The Manual will also instruct the pharmacist regarding preparation time before the start of the IV infusion on each infusion day, which should be as short as possible to assure maintenance of sterility given need for compounding (infusions must be prepared each day).

7.3 *Storage, Handling and Dispensing*

Vials of OCR-002 will be sent to the participating clinical site Investigator using standard, monitored, cold shipping methods. A Study Drug Shipping and Accountability Log will be maintained for all study drug shipped to any participating clinical site. Study drug will be stored in a secure area at the investigative site to prevent unauthorized access. Vials of OCR-002 should be stored at controlled refrigerated conditions of 2-8°C. A pharmacist or designee will prepare the IV infusion of OCR-002. The infusion bags will be labeled by the pharmacist with the following as a minimum: study number, patient number, and dose.

7.3.1 **Accountability Procedures and Return or Destruction of Clinical Supplies**

All study drug supplies will be used only in this clinical study and must not be used for any other purpose. The Investigator and/or designated study pharmacist must ensure that the supplies are stored in a secured area, with access limited to authorized study personnel. The Investigator is responsible for the accountability of study drug, including reconciliation and record maintenance at the clinical study site. In accordance with all applicable regulatory requirements, the Investigator or designated site staff must maintain study drug accountability records throughout the study, including a record of the dates and amounts of study drug received, amount dispensed, and the amount unused.

A Drug Dispensing Log will be maintained and contain, at minimum, the following

information:

Identification of the patient for whom the infusion was prepared, including the patient identification number assigned for the study.

Date and quantity of drug prepared for each patient.

Any product accidentally or deliberately destroyed.

The inventory must be available for inspection during the study by the study monitor. All study drug supplies (used and unused) will be accounted for on the Study Drug Accountability Log.

Following reconciliation, the empty or partially used vials should be destroyed according to the standard operating procedures (SOPs) established by the study site or governing institution. The Investigator will document the destruction of any study drug supplies.

At the end of the study, unused drug supplies will be destroyed by the Investigator according to local procedures, provided that such disposition does not expose humans to risks from study drug. Records shall be maintained by the Investigator of any such disposition of study drug, which must show the identification and quantity of each unit disposed of, the method of destruction (taking into account the requirements of local law), and the person who disposed of study drug.

7.4 Timing of Dosing and Administration of OCR-002 Infusion

Study drug dosing should be initiated as soon as possible upon admission to the registry but only after obtaining informed consent, ensuring all eligibility criteria are confirmed to be met and completing the initial baseline evaluation period. The window between obtaining informed consent and initiation of OCR-002 infusion may be up to 32 hrs in order to complete any pre-study drug initiation requirements and/or to provide a time frame for study drug administration. Each cohort will receive a continuous infusion of OCR-002 for up to 5 days (between 0 to 120 hours).

7.5 Treatment Compliance

Staff of the clinical study unit will supervise the IV infusion of study drug. The date and time of infusion start, infusion stop, and the total volume administered will be documented in the source records. In the case of interruption of infusion for any reason, the study drug will not be restarted if more than 2 hours has elapsed. If for any reason the infusion is interrupted or stopped prior to the full administration, the times and circumstances of the interruption/stoppage will be recorded. It is anticipated that patients will continue to remain in the hospital for a minimum of three days after start of study.

7.6 Prior and Concomitant Medications

Throughout the study, the Investigator may prescribe concomitant medications deemed necessary to provide adequate supportive care. Standard therapy will include, but is not limited to, the administration of NAC, third generation cephalosporins, hypertonic saline and mannitol.

All concomitant medications taken during treatment must be recorded in the source documents and transcribed onto the appropriate pages of the CRF.

Concomitant administration of drugs known to interfere with renal excretion of phenylacetylglutamine or those medications that may induce hyperammonemia, such as **haloperidol, valproic acid and systemic corticosteroids, are prohibited during the study.**

Alternative ammonia modifying agents such as lactulose and rifaximin are not considered standard of care and their use is prohibited during the study period, as is the use of therapeutic hypothermia. However, spontaneous (non-induced) hypothermia of a mild-to-moderate degree does not require correction.

7.7 Precautions, Contraindications and Warnings

Adverse events should be treated in accordance with standard clinical practice. Appropriate emergency medication and equipment must be available during the confinement periods, together with personnel trained to deal with medical emergencies. The Investigator (or other co-investigator on the study team) must be readily available at all times until patients have completed the treatment period.

Prior to hospital discharge, patients will be evaluated to determine if there are any clinically significant changes from baseline. Patients with significant findings must remain in the hospital for further observation and/or treatment until the condition is either explained, resolved, or no longer requires close observation. Any patient who develops an SAE will be followed until a probable diagnosis and the relationship to study drug have been determined, and until the AE has resolved, no longer requires further follow-up, or a new chronic baseline has been established.

8 STUDY PROCEDURES BY STUDY DAY

The procedures and evaluations at each visit are outlined below.

8.1 Screening

Patients will be evaluated for entry into the study according to the stated inclusion and exclusion criteria. Individuals who are identified during screening as not eligible for the study need not complete all screening procedures. The reason for ineligible status will be documented on the Screen Failure Log.

The following procedures will be obtained or performed to evaluate each patient's general health and qualifications for participation in the study:

- Demographic information including gender, date of birth, race and ethnicity;
- Medical and medication history over the past 30 days, including prescription and non-prescription over-the-counter medications, herbal medications, vitamins, and minerals;
- Collection of blood for hematology, coagulation, clinical chemistry, ammonia* and in female patients, a pregnancy test**;

*** Venous sampling is the protocol-preferred method of collection for ammonia samples. Arterial ammonia samples will be accepted if this is the available method; however, this same method should be used for all subsequent ammonia samples for the patient.**

**Urine pregnancy test or blood human chorionic gonadotropin (hCG) is acceptable.

- Urinalysis***;
 - ***Urinalysis: dipstick plus microscopic evaluation of sediment, if clinically indicated.
- Physical examination, including height and weight (body mass index will be calculated based on these variable), and vital signs (systolic and diastolic blood pressure, pulse rate, respiratory rate, body temperature);
- 12-lead ECG;
- Neurological battery, including
 - Glasgow Coma Scale;
 - West-Haven Scale; and
 - O-Log Scale;
- Review inclusion and exclusion criteria; and
- Signed, written informed consent.

The start of the initial infusion may begin after obtaining signed informed consent; or, up to 32 h after obtaining consent should the time be necessary to complete any pre-study drug initiation requirements and/or to provide a time frame for study drug administration. Patients will be considered enrolled once the informed consent has been obtained, all eligibility criteria have been met, and the study drug infusion initiated.

8.2 Assessments at Baseline

- Collection of blood for hematology, coagulation, clinical chemistry, ammonia* and PK*;

***The ammonia and plasma PK samples must be taken not more than 8 hours prior to the start of the initial study drug infusion. Venous sampling is the protocol-preferred method of collection for ammonia samples. Arterial ammonia samples will be accepted if this is the available method; however, this same method should be used for all subsequent ammonia samples for the patient.**
- Vital signs and abbreviated physical exam;
- Neurological battery**, including
 - Glasgow Coma Scale;
 - West-Haven Scale; and
 - O-Log Scale;

****Neurological exams at the Baseline visit should be performed within 8 hours prior to the start of the initial study drug infusion.**
- 12-lead ECG;***

*****The ECG at the Baseline visit should be completed prior to the start of the initial study drug infusion.**

8.3 Assessments during Study Treatment

Treatment Day 1 - Time “0” (T0)

Treatment Day 1-T0 is the start of the initial study drug infusion. At this time, each patient will receive an initial infusion rate of OCR-002; thereafter, up and down titration decisions will be based on the patient's tolerance of the study drug infusion, no noteworthy side effects, as well as their Cohort dosing level assignment into the study. The following additional procedures and evaluations are conducted at Treatment Day 1-T0 once the study drug infusion begins:

- OCR-002 Initial Infusion:
Dose Levels 1 through 3: initial infusion rate of 0.139 g/hour for the first 12 hours; continuation at this infusion rate for more than the first 12 hours is dependent on the patient's tolerance of the infusion, no noteworthy side effects, and the patient's Cohort dosing level assignment.
Dose Level 4: initiate infusion rate at the full dose level of 20g/24h (approximately .83g/h) without further dose escalation for a maximum time of 120 hours provided the dose level is well tolerated with no noteworthy side effects.
- Urinalysis*;
*Urinalysis: dipstick plus microscopic evaluation of sediment, if clinically indicated.
- Begin 0-12h urine collection interval;
- Collection of concomitant medications (if applicable);
- Continuous monitoring and collection of mean arterial pressure;
- Continuous monitoring and collection of intracranial pressure (ICP) (if applicable); and
- Begin continuous AE review and reporting.

Each event scheduled for this time point and subsequent time points during the treatment period has a collection window of +/- 3 hours with reference to Treatment Day 1-T0 as time of start of initial study drug infusion, with the exception of ammonia sampling, which has a collection window of +/- 1 hour.

Treatment Day 1 at 6 hrs

- Ammonia collection;
- Collection of concomitant medications (if applicable);
- Continuous monitoring and collection of mean arterial pressure;
- Continuous monitoring and collection of intracranial pressure (ICP) (if applicable);
- Document urine volume; and
- AE review and reporting.

Treatment Day 1 at 12 hrs

- OCR-002 Infusion for Dose Level 2 (the infusion rate will increase to 0.277 g/hour for the remainder of the study; for Dose Level 3, the infusion rate will increase to 0.277 g/hour for the next 12 hours), provided previous dose levels are well tolerated with no noteworthy side effects and the patient's Cohort dosing level assignment.

Dose Level 4 - continue on maintenance infusion of OCR-002;

- Collection of concomitant medications (if applicable);
- Collection of blood for hematology, coagulation, clinical chemistry, ammonia and PK;
- Vital signs and abbreviated physical exam;
- Neurological battery, including
 - Glasgow Coma Scale;
 - West-Haven Scale; and
 - O-Log Scale;
- Continuous monitoring and collection of mean arterial pressure;
- Continuous monitoring and collection of intracranial pressure (ICP) (if applicable);
- 12-lead ECG*;

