***The ECG should be completed prior to study drug escalation on Treatment Day 1 at 12 Hours (Dose Levels 2 and 3).**

- Document urine volume, take a sample from 0-12h urine volume, and begin 12-24h collection interval; and
- AE review and reporting.

Treatment Day 1 at 18 hrs

- Ammonia collection;
- Continuous monitoring and collection of mean arterial pressure;
- Continuous monitoring and collection of intracranial pressure (ICP) (if applicable); and
- AE review and reporting.

End of Treatment Day 1 at 24 hrs / Day 2 at 0 h

- OCR-002 Infusion for Level 3 dosing only (the infusion rate will be increased to 0.416 g/hour for the remainder of the study), provided previous dose levels are well tolerated with no noteworthy side effects and the patient's Cohort dosing level assignment.
Dose Level 4 - continue on maintenance infusion of OCR-002;
- Collection of concomitant medications (if applicable);
- Collection of blood for hematology, coagulation, clinical chemistry, ammonia and PK;
- Urinalysis*;
*Urinalysis: dipstick plus microscopic evaluation of sediment, if clinically indicated.
- Vital signs and abbreviated physical exam;
- Neurological battery, including
 - Glasgow Coma Scale;
 - West-Haven Scale; and
 - O-Log Scale;
- 12-lead ECG**;

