11.7.5 Physical Exams

Physical examination findings at baseline will be listed. Clinically significant changes will be recorded as AEs. Symptoms of interest previously reported with OCR-002 will be recorded daily, including dizziness, headache, nausea, vomiting; daily monitoring of heart rate in relation to infusion initiation will also be recorded.

11.7.6 Plasma Ornithine, Phenylacetate, Phenylacetylglutamine and Glutamine Concentrations and Pharmacokinetic Parameters

Individual and mean plasma ornithine, phenylacetate, and PAGN concentrations at each sampling time point will be presented by listings and descriptive summary statistics. Plasma ornithine, phenylacetate, and PAGN concentration versus time profiles will be plotted.

In addition, individual and mean cumulative urinary PAGN output will be listed with descriptive statistics in tabular format.

Pharmacokinetic parameters will be calculated from plasma ornithine, phenylacetate, and PAGN. Individual plasma ornithine, phenylacetate, and PAGN parameters will be listed for each patient and summary statistics will be provided.

The following PK parameters will be calculated or derived from the data:

- Maximum observed plasma concentration (C_{max});
- Concentration at steady state (C_{ss});
- Clearance at steady state (CL_{ss}); and
- Interval estimates of exposure (e.g. AUC_{0-24h}) over multiple dosing days.

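### PK samples at 12 h and 24 h may be drawn up to 3 h after a rate increase, so in Dose Levels 2 and 3 they can mix two infusion rates and bias any run-in Css or CLss

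*Combined protocol and SAP*

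**What the plan says.** Section 8.3 counts all treatment-period times from the start of infusion and gives a general rule: "Each event scheduled for this time point and subsequent time points during the treatment period has a collection window of +/- 3 hours". The single carve-out is "with the exception of ammonia sampling, which has a collection window of +/- 1 hour". PK has none.

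Dose Levels 1 to 3 start at 0.139 g/h. At 12 h the rate goes to 0.277 g/h in Levels 2 and 3. At 24 h the entry reads "OCR-002 Infusion for Level 3 dosing only (the infusion rate will be increased to 0.416 g/hour for the remainder of the study". The same visits list "Collection of blood for hematology, coagulation, clinical chemistry, ammonia and PK", with no order relative to the rate change.

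An order is given for one assessment only: "The ECG should be completed prior to study drug escalation on Treatment Day 1 at 12 Hours (Dose Levels 2 and 3"). A similar ECG footnote stands at 24 h.

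Section 11.7.6 plans individual and mean plasma concentrations by sampling time, and lists Cmax, Css, CLss and interval AUC. It does not say which samples or which rate define Css and CLss, and it does not mention actual draw times. Section 7.5 names infusion start, stop and total volume as items to record, but not the time of a rate change. The closing memorandum says that no separate SAP was compiled, so Section 11 is the whole plan.

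**The concern.** A PK sample taken 3 h into the higher rate complies with the protocol and is still filed as the 12 h or 24 h sample. PK draws during infusion are at 12, 24, 36, 48, 72 and 96 h and at the end of infusion. Within a patient, 12 h is thus the only PK time at 0.139 g/h in Levels 2 and 3, and 24 h is the only one at 0.277 g/h in Level 3. A late draw has no backup.

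Two outputs are exposed. The mean at 12 h or 24 h can combine patients sampled before and after the increase, even if the table is split by dose level. And if Css or CLss is reported for the run-in rate, a post-increase sample overstates the first and, over the half-lives considered below, understates the second. Steady-state PK is a secondary objective, and each dose step within a cohort has about three patients, so one late sample carries weight.

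**Working it through.** **Inputs from the documents.** Rates are 0.139, 0.277 and 0.416 g/h (Sections 5.2 and 8.3). Times 24 h, these give 3.34, 6.65 and 9.98 g, which reproduces the stated 3.33, 6.65 and about 10 g/24h. The steps are 0.277/0.139 = 1.993 and 0.416/0.277 = 1.502. The window is 3 h.

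**Assumptions.** The documents give no half-life. I take h = 1, 2 and 4 h, with a one-compartment linear model. The Section 4.1.2 hypothesis of steady state within 6-12 h is compatible: read as five half-lives it implies 1.2-2.4 h, and read as 90% of steady state it implies 1.8-3.6 h. That hypothesis concerns 10-20 g/24h, so applying it to the run-in rates is a further assumption.

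**Formulae** (superposition; the rate is taken to change exactly on schedule):
- 15 h, relative to Css at 0.139 g/h: (1 - 2^(-15/h)) + 0.993 x (1 - 2^(-3/h)).
- 27 h, relative to Css at 0.277 g/h: [0.139 x (1 - 2^(-27/h)) + 0.138 x (1 - 2^(-15/h)) + 0.139 x (1 - 2^(-3/h))] / 0.277.
- CLss error = 1/ratio - 1.

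Example, h = 2: at 15 h, 0.994 + 0.642 = 1.636, so the CLss error is 1/1.636 - 1 = -39%. At 27 h, 0.997 + 0.324 = 1.322, so the error is -24% (-25% if full steady state before the step is assumed).

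| Half-life (assumed) | On-time 12 h / Css | 15 h / Css | CLss error | On-time 24 h / Css | 27 h / Css | CLss error |
|---|---|---|---|---|---|---|
| 1 h | 1.00 | 1.87 | -46% | 1.00 | 1.44 | -31% |
| 2 h | 0.98 | 1.64 | -39% | 0.99 | 1.32 | -24% |
| 4 h | 0.875 | 1.33 | -25% | 0.93 | 1.16 | -14% |

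**Effect on a mean of three.** If one of three patients is drawn 3 h late, the 12 h mean rises by one third of the excess over an on-time draw: 29%, 22% and 17% for h = 1, 2 and 4. At 24 h the rise is 15%, 11% and 8%.

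**Longer half-lives.** At 6-12 h, an on-time 12 h draw is itself only 75% to 50% of Css, so no Css can be read from it. The late draw still reads 47-49% above the on-time one at 12 h, and 22-23% above at 24 h. The mixing in the mean remains, but the bias against Css no longer has a fixed sign.

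**Final rate.** Dose Level 3 at 48 h is within 0.6% of Css for half-lives up to 4 h.

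**The case against.** The strongest reply is that the affected quantity may never be reported. Section 11.7.6 does not say that Css or CLss is computed at a run-in rate. The steady-state hypothesis concerns 10-20 g/24h, meaning Level 3's final rate and Level 4, which have several samples away from any planned increase. The lower rates are also observed without a nearby step: 0.139 g/h throughout Level 1, and 0.277 g/h after 12 h in Level 2. All of this stands and limits the point. It does not remove the planned mean by sampling time, or the lack of a second within-patient sample at the earlier rate.

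Three stronger readings are tempting and not supported:
- A reader might infer that SRC escalation decisions rest on contaminated values. The SRC reviews PK between dose levels, when final-rate samples exist, and the within-patient steps depend on tolerability. No passage ties a decision to the 12 h or 24 h concentration.
- A reader might infer that ammonia suffers equally. Its window is 1 h, and it is also sampled at 6 h and 18 h, well inside the intervals at 0.139 and 0.277 g/h.
- A reader might infer that the bias is irrecoverable. With actual draw and rate-change times, a model could use late samples correctly. The protocol does not require those times or such a model.

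The percentages are also for the latest permitted draw, not a typical one. A simple rate-over-concentration clearance does not suit PAGN, which is a metabolite.

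**Conclusion.** The point holds in limited form. The window allows the 12 h PK sample (Levels 2 and 3) and the 24 h sample (Level 3) to be taken at the wrong rate, and nothing else in the plan prevents or corrects this. If such a sample were used for the earlier rate, CLss would be understated by up to about 46%, 39% or 25% at 12 h and 31%, 24% or 14% at 24 h, for assumed half-lives of 1, 2 or 4 h under linear kinetics. Final-rate Css and CLss, Dose Levels 1 and 4, and the primary safety objective are essentially untouched. This is an inexpensive improvement to a descriptive PK analysis, not a threat to the trial's main conclusions.

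One inconsistency needs separate attention. The 24 h ECG footnote refers to an escalation in Dose Levels 2 and 3, while the infusion entry for the same time is for Level 3 only. These passages must be reconciled.

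**What to change.** - **Section 8.3:** at 12 h (Dose Levels 2 and 3) and 24 h (Dose Level 3), schedule the PK and ammonia draw before the rate increase, alongside the ECG, with a short window such as within 1 h before, in place of +/- 3 h. This moves the draw, not the rate change.
- **Section 7.5 and the CRF:** record the actual time of each PK draw and each rate change.
- **Section 11.7.6:** state that a sample drawn after the change is not assigned to the earlier rate, and that Css and CLss come from samples at a stable rate. For samples already taken, apply the same rule wherever actual times exist.

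The cost is a slightly tighter draw window, with no extra sample or visit. Some error remains because steady state may be incomplete. A draw 1 h early overstates CLss by about 0%, 2% or 17% at 12 h for half-lives of 1, 2 or 4 h, and by 0%, 1% or 9% at 24 h. The present window already permits a 9 h draw, which at a 4 h half-life overstates CLss by 27%, so the change adds no early-draw error.
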